3.3.2 Follow-up for withdrawn subjects

If participants are withdrawn from the study for any of the reasons noted above prior to randomization, they will be replaced until a total of 240 participants have been randomized to the study. Subjects who withdraw themselves or are withdrawn from the study at a visit will be asked to complete the study visit including a questionnaire regarding the reasons for dropping out.

For participants who withdraw themselves from the study, they will be asked if we can follow up with them at the week 16 visit. We will contact them via one call, message, and letter to complete the week 16 visit. If they wish not to be contacted to complete the week 16 visit, they will not be contacted.

If participants are lost to follow-up (i.e. simply do not respond to calls or letters without formally withdrawing) one final attempt will be made to contact them for the week 16 visit via one call, message and letter. If they complete the week 16 visit they will also be invited to the final (week 20) visit.

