8.0 Subject Numbers and Statistical Plan

8.1 Number of Subjects

We plan to enroll 300 participants in order to randomize 240 participants (60 in each of the four study arms).

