8.2 Sample size determination

For the sample size calculation, we have used data for completers of our recent randomized controlled trial(8) to estimate magnitude of effects for the primary endpoint (NNAL, pmol/mg creatinine). Additionally, we have used data from Donny et al.'s trial [Table Supplement 15] (5). Based on their paper, the difference in log NNAL between the 0.4 mg/g group (sample size 96) and the 15.8 mg/g group (sample size 100) is $\log(0.78) = -0.248$ with a confidence interval of $\log(c(0.64, 0.96)) = (-0.446, -0.0408)$. Based on this, the within group standard deviation of log NNAL is 0.562. Combining the above two datasets, we shall assume that the effect size is 58% of the size of the standard deviation in the sample size calculation, slightly larger than reported above because our trial will have 16 weeks of follow-up. Let arm 3 of the trial be the group to which arms 1, 2 and 4 will each be compared. To adjust for multiple comparisons, the type one error level alpha is taken to be $.05/3=0.017$. The sample size of 60 subjects in each of the 4 arms is needed to provide 80% power of detecting a difference between any three arms and arm 3. In addition this trial will have over 95% power, at a 5% type 1 error rate, to detect the same effect on abstinence found in our recent RCT of VLNCs one month after the end of the randomized phase (20.2% in those randomized to VLNCs vs. 6.4% in those randomized to NNCs).

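### Section 3.3.2 arranges a week-16 contact for participants who leave or are lost, but none for randomised participants the investigator withdraws before Visit 7, so their primary NNAL value is missing by default

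*Combined protocol and SAP*

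**What the plan says.** Section 3.3.2 treats those who stop early as follows.

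- **Withdrawn before randomisation:** replaced. The text reads "prior to randomization, they will be replaced until a total of 240 participants have been randomized to the study". No replacement is stated after randomisation.
- **Withdrawn at a visit, by self or by the investigator:** "Subjects who withdraw themselves or are withdrawn from the study at a visit will be asked to complete the study visit", together with a questionnaire on the reasons.
- **Self-withdrawn:** "For participants who withdraw themselves from the study, they will be asked if we can follow up with them at the week 16 visit". One call, one message and one letter follow, unless the person declines.
- **Lost without formally withdrawing:** one final week-16 attempt by the same three routes. The paragraph then adds: "If they complete the week 16 visit they will also be invited to the final (week 20) visit".

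Section 3.3.1 lists many reasons for which the investigator may withdraw a randomised participant. They include a combined rise in cigarettes per day and CO, adverse events related to the e-cig, raised blood pressure, certain hospitalisations (worsening psychiatric symptoms are given as one example), suicide attempt, new pregnancy and conduct.

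Section 1.2 makes week-16 urinary NNAL the primary endpoint. Section 8.3 analyses NNAL only by ANCOVA of the Visit 7 value with the Visit 3 value as covariate, and adopts the intention-to-treat principle.

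**The concern.** Section 3.3.2 itself distinguishes people who withdraw from people who are withdrawn. It gives both groups the same instruction for the current visit, then gives the later week-16 contact to the first group only. A randomised participant withdrawn by the investigator at, say, Visit 4 has no stated route to a week-16 urine sample.

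NNAL is the endpoint least able to absorb this. Measures taken at every visit can contribute earlier values to the mixed model in Section 8.3, but that section confines NNAL to the two-time-point ANCOVA. Without a Visit 7 sample the participant contributes nothing to the primary comparison. A sample not requested in time cannot be collected later.

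Two things are at stake. One is a small loss of precision. The other is selection after randomisation: a rise in smoking and CO, e-cig adverse events or psychiatric worsening could each occur more often under one assigned product than another, so those removed may differ systematically between arms.

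**Working it through.** **Step 1. Does any other section fill the gap?**

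| Place | What it provides | Week-16 NNAL for this group? |
|---|---|---|
| 3.3.2, withdrawal at a visit | Completion of that visit | Only if that visit is Visit 7 |
| 3.3.2, self-withdrawn | Call, message, letter | No: limited to those who withdraw themselves |
| 3.3.2, lost to follow-up | Call, message, letter | No: limited to those who have not formally withdrawn |
| 7.1 and 7.2, follow-up of all participants | Week-20 visit | No: no NNAL urine is scheduled there |
| 7.2, missed visits and data by phone | Rescheduling attempts; phone data | No: withdrawn participants are not mentioned, and a call cannot supply urine |

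As far as the extracted layout shows, Table 1 places NNAL urine at Visits 3, 5 and 7. Someone withdrawn at Visit 5 should therefore still give a week-8 sample, but the NNAL model does not use it.

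**Step 2. Is there stated slack?** Section 8.1 says "We plan to enroll 300 participants in order to randomize 240 participants (60 in each of the four study arms", so the 300-to-240 margin is used up before randomisation. Section 8.2 says "The sample size of 60 subjects in each of the 4 arms is needed to provide 80% power", which is the number randomised.

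**Step 3. Reproduce the plan's power.** Inputs:
- Effect d = 0.58 (Section 8.2: "we shall assume that the effect size is 58% of the size of the standard deviation").
- Alpha 0.05/3 per comparison (Section 8.2).
- Two-sided tests (Section 8.3).
- n = 60 per arm.

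The normal approximation gives 78.3% (78.5% with alpha rounded to 0.017), within 2 points of the stated 80%. The noncentral t gives 77.2%.

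**Step 4. Effect of losing NNAL values.** The documents give no number of investigator withdrawals. Losses of 1 and 3 per arm are assumptions. For an unadjusted two-sample t-test, λ = d√(n/2) with 2n − 2 degrees of freedom. The standard error relative to 60 per arm is √(60/n).

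| Analysed per arm | λ | Critical t | Power | Change | SE ratio |
|---|---|---|---|---|---|
| 60 | 3.177 | 2.429 | 0.772 | – | 1.000 |
| 59 | 3.150 | 2.429 | 0.763 | −0.8 points | 1.008 |
| 57 | 3.096 | 2.430 | 0.746 | −2.5 points | 1.026 |

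**Step 5. Allow for the baseline covariate.** The planned ANCOVA raises the effective d to 0.58/√(1 − ρ²). The documents give no correlation ρ, so the values below are assumptions.

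| Assumed ρ | Power at 60 | Power at 57 | Change |
|---|---|---|---|
| 0.3 | 81.5% | 79.1% | −2.4 points |
| 0.5 | 89.1% | 87.2% | −1.9 points |
| 0.7 | 97.7% | 97.0% | −0.7 points |

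**Step 6. Scale of possible bias (illustration only).** Suppose a share m of one arm is missing, their values differ from the rest of that arm by s SD, and nothing offsets this in the comparator. The contrast then shifts by m × s. With m = 3/60 = 0.05 and s of 0.25, 0.5 or 1.0, the shift is 0.0125, 0.025 or 0.05 SD, that is 2.2%, 4.3% or 8.6% of 0.58. Neither m nor s can be taken from the documents.

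**The case against.** The best defence is that this is a reasonable design choice with little to recover. Many reasons in Section 3.3.1 concern safety or conduct: a suicide attempt, a cardiovascular hospitalisation, threatening behaviour, selling product. The protocol may intend to distinguish people who choose to leave from people who had to be removed, and inviting some of the latter back would be inappropriate. The power figures count the full loss, while only part is retrievable, and baseline adjustment may make even the full loss cheaper. All of this stands, and it sets the grade. It does not close the gap: other triggers, such as raised blood pressure, need not prevent a later urine sample, and the protocol gives no reason for omitting the request.

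A reader might also infer more than the text supports:

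- **That contact is forbidden.** Section 3.3.2 is silent. The loss follows from carrying out the plan as written, not from a prohibition.
- **That the primary result will be materially biased.** No withdrawal count, arm difference or NNAL difference is given. That some triggers could depend on product is plausible, not shown. Nor do the documents support confining the possibility to the smoking-and-CO trigger.
- **That this gap explains power below 80%.** The 77.2% arises at a full 60 per arm and has nothing to do with withdrawals.
- **That the absence of a missing-data method or attrition allowance is part of this point.** Both affect every missing week-16 value, whatever the cause, and would remain after Section 3.3.2 was corrected.

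**Conclusion.** The point holds as a minor one. Section 3.3.2 leaves one group of randomised participants, those withdrawn by the investigator before Visit 7, without a stated request for primary-endpoint data, and no other section supplies it. They are missing from the NNAL ANCOVA by default for reasons arising after randomisation, which sits poorly with the stated ITT principle.

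The size is probably small. On assumed losses of 1 to 3 per arm, the cost is at most about 0.8 to 2.5 points of power and a standard error larger by 0.8% to 2.6%. The benefit of the fix is less than that, by an amount that cannot be determined. Bias is possible but cannot be sized. These figures rest on the plan's 0.58 SD and alpha of 0.05/3, on an unadjusted comparison, and on assumed counts.

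**What to change.** In Section 3.3.2, extend the existing week-16 contact (one call, message and letter) and the week-20 invitation to randomised participants withdrawn by the investigator who agree to it, except where the investigator judges a visit unsafe or inappropriate. In Section 8.3, state that values so obtained enter the ITT ANCOVA in the arm assigned, as a treatment-policy comparison, and that withdrawals will be reported by reason and arm. Leave all withdrawal and product-management rules as they are.

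The cost is a short protocol and consent amendment, a few extra contacts, and staff and assay time that the documents do not price. The payment table in Section 13.0 gives $80 for Visit 7 and $90 for Visit 8, so at most $80 + $90 = $170 for each participant who completes both. That is already part of the $550 each participant could earn. The yield will be partial, since some will decline and the safety exception will remove others.

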1.0 Objectives

1.1 Study Objectives

The long term goal of this project is to determine the likely health effects of very low nicotine content in cigarettes, in conjunction with availability of nicotine-containing electronic cigarettes (e-cigs) among smokers with mental health conditions (SMHC). This will be tested in a rigorous randomized controlled trial design. We plan to use a comprehensive set of measures of proven validity and reproducibility, including toxicant exposure, addiction and mental health to assess these effects. The specific objective of this study is to recruit a cohort of 240 current exclusive daily SMHC (diagnosed using the MINI International Neuropsychiatric Interview) and to measure a comprehensive battery of behavioral and health indicators at 4 and 8, 12 and 16 weeks after being randomized to use either normal nicotine content (NNC) Spectrum cigarettes (11.6 mg nicotine/cigarette) or very low nicotine content (VLNC) Spectrum cigarettes (0.2 mg nicotine/cigarette) while also having access to a JUUL e-cig (JUUL Labs, Inc.) containing either 0% or 5% nicotine strength e-liquids in a randomized double-blind, placebo-controlled 2 by 2 design. Our central hypothesis is that key markers of harms to health (e.g. urinary NNAL, exhaled CO, measures of addiction, and mental distress) will be significantly improved among SMHC who are provided very low nicotine cigarettes and high nicotine e-cigs. Study aims are:

Aim 1: To determine whether SMHC have lower levels of markers of harm (e.g. urine NNAL, exhaled CO, measures of mental health) and cigarette addiction when switched to VLNC cigarettes, as compared with NNC cigarettes, at the end of the randomized phase (week 16).

Aim 2: To determine whether SMHC have lower levels of markers of harm (urine NNAL, exhaled CO) and cigarette addiction when provided with nicotine-containing versus zero nicotine electronic cigarettes, at the end of the randomized phase (week 16).

Aim 3: To determine whether use of VLNC cigarettes increases the proportion of smokers who completely switch away from combustible tobacco use (no cigarette use in the past 7 days and CO < 6ppm), as assessed (a) at the end of the randomized phase (week 16) and (b) 4 weeks after the end of the randomized phase of the trial (week 20), compared to those using NNC cigarettes.

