1.3 Secondary Study Endpoints

Secondary endpoints include exhaled CO, Kessler-6 score, and cigarette/e-cigarette dependence using Penn State Cigarette Dependence Index (PSCDI) and Penn State Electronic Cigarette Dependence Index (PSECDI), at week 16, and cigarette abstinence (no cigarette use in the past 7 days and CO < 6ppm) at week 20.

Additional endpoints include:

Health effects and toxicant exposure measures: Pulmonary Function Tests (PFT), Clinical COPD Questionnaire (CCQ), urinary CYMA (biomarker for acrylonitrile [volatile organic compound] exposure), 3HPMA (biomarker for acrolein [volatile organic compound] exposure, cotinine (biomarker of nicotine exposure)

Mental health measures: Center for Epidemiological Studies-Depression (CES-D), Overall Anxiety Severity and Impairment Scale (OASIS), Quick Inventory or Depressive Symptomatology (QIDS), Perceived Stress Scale (PSS)

Nicotine/Tobacco use and addiction measures: daily cigarette use, daily e-cig use, Fagerstrom Test for Nicotine Dependence (FTND), Hooked on Nicotine Checklist (HONC), , Minnesota Nicotine Withdrawal Scale (MNWS)

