7.0 Study Design and Procedures

7.1 Study Design

We propose to conduct a parallel-group, randomized, double-blind, 2-by-2 controlled trial in which 240 current SMHC will be randomized to one of 4 groups: 1) normal nicotine content cigarettes (NNCs) and nicotine containing e-cigs; 2) NNCs and zero nicotine e-cigs; 3) very low nicotine content cigarettes (VLNCs) and nicotine containing e-cigs 4) VLNCs and zero nicotine e-cigs.

After baseline phases on own cigarettes (one week) and NNCs (2 weeks), participants will be randomized to one of these four groups and will attend visits every 4 weeks for 16 weeks, at which point the main study outcome measures will be assessed. All participants will be followed up with a study visit 4 weeks after the final randomized visit to identify whether they have continued to use e-cigs/cigarettes and to assess their motivation in smoking abstinence.

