All participants will be followed up at a visit 4 weeks after their last visit of the Randomized Phase in order to find out their cigarette/e-cig consumption and any attempts in abstinence after participating in the randomized portion of the trial. Participants will return any final e-cigs and e-liquid pods to the study team by either dropping them off to the researcher or scheduling a pick up time with the researcher. If neither of these options can be arranged the participants will be advised how to properly dispose the products themselves. Participants will complete an exhaled CO measurement plus all measures listed in Table 1. Participants will be compensated for completing the study visit procedures.

Procedures during COVID-19:

Remote Visit 8 will be completed remotely over Zoom or the telephone. All participants will be followed up 4 weeks after their last visit of the Randomized Phase in order to find out their cigarette/e-cig consumption and any attempts in abstinence after participating in the randomized portion of the trial. Questionnaires for visits outlined in Revised Table 1 will be sent to the participant via a survey link before the in-person visit. Participants will be encouraged to complete the questionnaires 2 hours before the visit, but will have up to 24 hours to complete them after the visit. Participants will return their e-cig and any e-liquid pods in a pre-paid envelope addressed to the study site. In cases where participants report being abstinent from cigarettes in the past 7 days at Visit 8, we will verify with a carbon monoxide reading (which biochemically validates abstinence). We will plan to send individual CO monitors for participants that can be mailed to the participant's house. Participants will use the personal devices to complete a CO measurement while on ZOOM with the researcher. Participants will be compensated for completing the study visit procedures.

Unscheduled Visits

If a participant requires additional study product (e.g., cigarette packs, e-cig pods), or if the e-cig fails, they may call the research center to schedule a time to obtain additional products (in-person).

Appointment Reminders

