Phone call, text, and email reminders will be used throughout the study to remind participants of their next visits (approximately 1-2 days prior). Also, visit time/date confirmation and study center directions will be emailed/mailed to the participant prior to Visit 1 (see First Appointment Reminder document). For participants who allow us to contact them through phone and text messaging, the study team will be using Google Voice to call or text participant reminders of the study visit and reminders to complete the study surveys with the REDCap survey link. Google Voice is phone service that allows researchers to communicate with participants without revealing their personal phone numbers. The study team will save participants phone number with their study ID. Participants will be told not to share PHI through this phone number.

Biospecimen Processing

All urine samples collected will be stored and analyzed in the project biomarkers core lab led by [name].

Data Collection via Phone

If participants are unable to attend an in-person study visit, the researcher will attempt to collect data over the phone. Participants will not be compensated for data provided through this method.

Missed Visit Procedures

Participants will be called at least once to reschedule a missed Visit 1. For participants who do not show up for any other in-person visit, up to 3 phone/email attempts will be made to contact them to reschedule their appointment.

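### Section 3.3.2 makes week-20 follow-up of lost participants conditional on week 16 and gives withdrawn participants no stated route to it, while 7.1 and 7.2 promise it for all

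*Combined protocol and SAP*

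**What the plan says.** **What the aim needs.** Aim 3(b) in section 1.1 sets the assessment at week 20, and section 1.3 lists as a secondary endpoint "cigarette abstinence (no cigarette use in the past 7 days and CO < 6ppm) at week 20". Section 8.3 adopts intention to treat for its two analysis approaches and says tobacco-use measures will be compared in a similar way. It gives no rule for missing abstinence.

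**What 3.3.2 provides for people who leave after randomisation.**
- Lost to follow-up: "one final attempt will be made to contact them for the week 16 visit via one call, message and letter". Then: "If they complete the week 16 visit they will also be invited to the final (week 20) visit".
- Self-withdrawn: "they will be asked if we can follow up with them at the week 16 visit". Week 20 is not mentioned, even for those who agree and attend.
- Withdrawn by the investigator (reasons in 3.3.1): asked to complete the visit at which they are withdrawn. Nothing later is stated.

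**What the design and procedures provide.** Section 7.1: "All participants will be followed up with a study visit 4 weeks after the final randomized visit". Section 7.2, Follow-up Visit 8 (Week 20): "All participants will be followed up at a visit 4 weeks after their last visit of the Randomized Phase".

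**The concern.** An intention-to-treat comparison of week-20 abstinence needs that status sought from everyone randomised. Section 3.3.2 is the text written for people who leave early, and it seeks week 20 from only some of them. For lost participants the gate is week-16 attendance, which comes after randomisation and could be affected by the assigned cigarette.

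Either way of handling the resulting gaps has a cost. If missing is counted as smoking, a quitter who stopped attending is recorded as a smoker and the contrast is diluted. If missing cases are dropped, the comparison is restricted to attenders and may be biased in either direction. Part of this loss is avoidable, because abstinence needs self-report and a CO reading, not a urine sample.

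**Working it through.** **Step 1. The passages side by side.**

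| Participant | 3.3.2 | 7.1 and Visit 8 in 7.2 |
|---|---|---|
| Lost, completes week 16 after the final attempt | Invited to week 20 | Followed up |
| Lost, does not complete week 16 | No invitation stated | Followed up |
| Self-withdrawn | Week 16 only, if permitted | Followed up |
| Withdrawn by the investigator | Nothing after the withdrawal visit | Followed up |
| Enrolled, misses Visit 7 | Not covered | Followed up; missed-visit procedures apply |

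Rows 2 to 4 disagree. Rows 1 and 5 do not.

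**Step 2. The plan's own power figure.** Inputs: 20.2% against 6.4% (section 8.2); 60 per arm (8.1), so n = 120 per cigarette group; two-sided 5% (8.3). With p̄ the mean of the two rates,

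power = Φ{ [(p1 − p2) − 1.96·√(2p̄(1−p̄)/n)] / √[(p1(1−p1) + p2(1−p2))/n] }.

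Here p̄ = 0.133, the null standard error is 0.0438 and the alternative standard error is 0.0429. So (0.138 − 0.0859)/0.0429 = 1.21, and power is 88.7%. Section 8.2 states over 95%, which is not reproduced. Other two-sided methods give 84.6% (continuity-corrected), 86.2% (Fisher exact), 89.5% (unpooled) and 90.3% (arcsine). That is a separate matter; 88.7% is the reference here.

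**Step 3. Loss at week 20 (assumed range).** The 300-to-240 allowance in 8.1 covers loss before randomisation, and no later loss rate is stated. Let m be the share unassessed in both groups, with missing counted as smoking and quitting unrelated to attendance. The rates become 0.202(1−m) and 0.064(1−m).

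| m | Rates | Difference (points) | Power |
|---|---|---|---|
| 0 | 20.2% vs 6.4% | 13.8 | 88.7% |
| 10% | 18.2% vs 5.8% | 12.4 | 84.7% |
| 20% | 16.2% vs 5.1% | 11.0 | 79.6% |
| 25% | 15.2% vs 4.8% | 10.4 | 76.6% |

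**Step 4. How much of that belongs to the rule.** Only people who would respond at week 20 if invited, and are not invited, are lost because of 3.3.2. If they are a share r of those unassessed, the rule removes 13.8 × m × r points. At m = 20% that is 2.8 points if r = 1, 1.4 if r = 0.5 and none if r = 0. In power terms, r = 0.5 would move the 20% row to the 10% row (79.6% to 84.7%). The documents give neither m nor r.

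**Step 5. Direction if missing cases are dropped.** Illustration with assumed unequal loss: 30% with very low nicotine cigarettes, 10% with normal nicotine cigarettes, all the missing being smokers. Then 0.202/0.70 = 28.9% and 0.064/0.90 = 7.1%, a difference of 21.7 points (before rounding) instead of 13.8. Such an analysis could overstate the effect as easily as dilute it.

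**Step 6. A check on Step 3.** 19/94 = 20.2% and 6/94 = 6.4%, and section 2.2 reports the earlier trial's final quit rates by intention to treat with 94 per group. If the planning rates already count missing as smoking, similar loss is already built in, and power stays near 88.7%.

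**The case against.** A reader might infer that week-20 abstinence is never sought from anyone who misses week 16. The documents do not support that. The conditional sentence covers only people who have stopped responding. For someone still enrolled who misses Visit 7, section 7.2 provides that "For participants who do not show up for any other in-person visit, up to 3 phone/email attempts will be made to contact them", allows data collection by phone, and nothing there bars Visit 8.

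A reader might also take the Visit 8 wording literally and conclude that someone last seen at week 8 is due at week 12. That is strained: the visit is headed Week 20, Revised Table 1 places it there, and Aim 3(b) equates the time point with week 20. Even literally, it would mean contact at the wrong time, not no contact. The wording is worth tidying but is not evidence of missing follow-up.

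Nor is it certain that a site cannot follow both rules. Section 3.3.2 can be read as a specific exception to a general statement. But on that reading the exception is exactly the conditional rule at issue.

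The strongest objection concerns size. People who have ignored repeated contact and a final call, message and letter may rarely answer at week 20, so most loss would be ordinary attrition that no wording removes. This stands, and it is why the power figures cannot be read as the effect of the rule.

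Finally, the remote Visit 8 with a mailed CO monitor appears only under the COVID-19 procedures, so it cannot be assumed available at other times.

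**Conclusion.** The point holds as a conflict between sections with a consequence for Aim 3(b). Section 3.3.2 makes week 20 conditional on week 16 for lost participants, states no week-20 route for self-withdrawn participants, and states no later follow-up for those the investigator withdraws. Sections 7.1 and 7.2 say all participants are followed up. Applied as written, 3.3.2 produces some avoidable missing data on a post-randomisation condition. It concerns a named aim and a secondary endpoint, not the primary endpoint.

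The size is unknown. The gap between 88.7% and 79.6% power at an assumed 20% loss is the most the fix could recover under the Step 3 assumptions: equal loss, quitting unrelated to attendance, missing counted as smoking, and everyone unassessed being recoverable. It shrinks with the share who would actually respond, and may vanish if the planning rates already include loss. The conflict between the sections depends on none of these numbers.

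**What to change.** 1. In 3.3.2, replace the conditional sentence with: *every randomised participant who has not refused further contact will be invited to the week-20 assessment, whether or not week 16 was completed.* This covers lost participants and those withdrawn by the investigator; any intended exceptions should be listed.
2. In 3.3.2, ask self-withdrawn participants for permission for both week 16 and week 20.
3. In 7.1 and under Visit 8 in 7.2, state the timing as week 20 after randomisation (Visit 3), so that all sections name the same date.
4. If remote CO verification is to be used outside the COVID-19 procedures, say so as an extension of that existing procedure.

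The cost is protocol wording, one more contact attempt per participant who missed week 16, and, if item 4 is adopted, an occasional mailed monitor. No new visit or assay is needed. These changes do not settle how missing abstinence is analysed; section 8.3 needs its own rule for that.
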